#### 13.7.2 Follow-up Requirements for Early Withdrawal

Subjects who are withdrawn due to toxicity or progressive disease will be followed for as long as they are receiving treatment for their HGG at the clinical center. Study visits will cease, however data collection for survival should continue at a minimum of three month intervals. For subjects who voluntarily withdraw, there is not an end of study visit, unless deemed appropriate by the PI. Early withdrawal subjects will be followed for survival where possible, except for subjects that specifically request not to have any further follow up.

### 13.8 Study Assessments

#### 13.8.1 Medical History

Standard medical history assessments will be conducted and recorded per institutional and sponsor guidelines.

#### 13.8.2 Physical and Neurological Examinations

Physical and neurologic examinations, vital signs (temperature, respiratory rate, blood pressure and pulse), height (screening only), weight and KPS must be performed at:

- screening
- day of loading dose (Arm A in Phase 2)
- two weeks after the completion of RT and TMZ
- every standard of care (SOC) clinic visit (approximately every 8 weeks) during adjuvant TMZ
- at the time of study completion

Additional physical and neurological examination may be performed every two weeks during standard RT and TMZ per the standard of care practice. More frequent examinations may be performed at the investigator's discretion, if medically indicated.

#### a. Physical examination, vital signs, weight and height

A complete Physical Examination (PE) will include a general physical examination of major body systems, temperature, respiratory rate, blood pressure, heart rate, body weight and height.

Height will be measured and documented at screening only.

Blood pressure should be measured per institutional guidelines.

#### b. Neurologic examination

A complete neurologic examination will include assessment of level of consciousness, mental status, speech, cranial nerves, motor, sensory, coordination, reflexes, and gait. Follow-up evaluation of the neurologic examination will be based on any changes in the neurologic clinical examination from the previous exam. Changes should be unrelated to postictal state or other unrelated events such as infection.

#### 13.8.3 Electrocardiogram (ECG)

ECG will be done for screening purposes for all subjects. For subjects in Arm A, a baseline ECG prior to BMX-001 administration will be completed and at 60 ( $\pm$ 15) minutes after dosing on the loading day of BMX-001 and on the first BMX-001 maintenance dose administration day during Week 1 and any

dose in Week 4 pre-dose and at 60 (±15) minutes after dosing. Results will be filed in the source for each subject and redacted tracings will be uploaded to the sponsor electronic database.

#### 13.8.4 Radiographic Response

The guidelines and criteria for radiographic response will be based on the RANO criteria. MRI brain with and without contrast will be obtained at baseline after standard RT and TMZ (within 2 to 4 weeks) and every standard of care (SOC) clinic visit (approximately every 8 weeks) during adjuvant TMZ. Institutional standard operating procedure will be followed (see Protocol Appendix A, Section 19.1). The clinical centers will be provided with a Clinical Trial Radiographic Assessment Form (CTRAF) to aid them with the data collection required for the study. A different form may be used with approval from the sponsor. RANO criteria will be utilizing based on the modifications from Ellingson et al. [66]. In these criteria, particularly in regards to newly diagnosed subjects, the areas considered in determining comprehensive objective status in RANO criteria are target lesions (enhancing disease), new sites of measurable disease, neurological examination status, and corticosteroid usage and dose.

Complete Response (CR): Requires all of the following:

- Disappearance of all enhancing measurable and nonmeasurable disease sustained for at least 4 weeks. The first scan exhibiting disappearance of all enhancing measurable and non-measurable disease is considered "preliminary CR". If the second scan exhibits measurable enhancing disease with respect to the "preliminary CR" scan, then the response is not sustained, noted as "pseudoresponse", PsR, and is now considered "preliminary PD" (note confirmed PD requires at least two sequential increases in tumor volume). If the second scan continues to exhibit disappearance of enhancing disease or emergence of non-measurable disease (less than 10mm bidimensional product), it is considered a durable CR and the patient should continue on trial until confirmed PD is observed.
- 2. Patients should be either off of corticosteroids or on physiologic replacement doses only.
- 3. Stable or improved neurological examinations.

Partial Response (PR): Requires all of the following

- 1. Greater than or equal to a 50% reduction in the size (products of the largest perpendicular diameters) for all enhancing lesions compared with baseline, sustained for at least 4 weeks. The first scan exhibiting greater than or equal to a 50% decrease in the sum of the products of the perpendicular diameters of all measurable enhancing lesions compared with the baseline is considered "preliminary PR". If the second scan exhibits PD with respect to the "preliminary PR" scan, then the response is not sustained, noted as pseudoresponse, PsR, and is now considered "preliminary PD" (note confirmed PD requires at least two sequential increases in tumor volume.) If the second scan exhibits SD, PR, or CR, it is considered a durable PR and the patient should continue on trial until confirmed PD is observed.
- 2. Patients should have either the same corticosteroid doses or on lower corticosteroid dose compared with baseline scan.
- 3. Stable or improved neurological examinations

Stable Disease: Evaluations that do not meet criteria for CR, PR or PD.

Progressive Disease: Defined as the following

1. Greater than or equal to a 25% increase in the product of the largest perpendicular diameters of any enhancing lesion or any new enhancing tumor on MRI scans. The first scan exhibiting greater than or equal to a 25% increase in the sum of the products of perpendicular diameter of the enhancing lesions should be compared to the smallest tumor measurement obtained either at baseline (if no decrease) or best response (on stable or increasing corticosteroid dose) and is

noted as "preliminary PD". If the second scan at least 4 weeks later exhibits a subsequent greater than or equal to 25% increase in the sum of products of perpendicular diameters of the enhancing lesions relative to the "preliminary PD" scan, it is considered "confirmed PD" and the patient should be discontinued from the study. If the second scan at least 4 weeks later exhibits SD or, PR/CR, this scan showing "preliminary PD" is noted as "pseudoprogression", PsP, and the subject should remain on study until a second increase in tumor size relative to the PsP scan is observed. Of note, any new measurable (> 10 mm X 10 mm) enhancing lesion should not be immediately considered PD, but instead should be added to the sum of the bidimensional products representing the entire enhancing tumor burden.

- 2. In the case where the baseline or best response demonstrates no measurable enhancing disease (visible or not visible), then any new measurable (>10mm x 10mm) enhancing lesions are considered PD after confirmed by a subsequent scan ≥4 weeks exhibiting greater than or equal to a 25% increase in sum of products of perpendicular diameters relative to the scan first illustrating new measurable disease. The first scan exhibiting new measurable disease is noted as "preliminary PD". If the second scan at least 4 weeks later exhibits a subsequent greater than or equal to a 25% increase in sum of products of perpendicular of enhancing lesions relative to the "preliminary PD" scan it is considered "confirmed PD" and the patient should discontinue therapy. If the second scan at least 4 weeks later exhibits SD, CR, PR, or becomes non-measurable, this scan showing "preliminary PD" is noted as "pseudoprogression", PsP, and the subject should continue on study until a second increase in tumor size relative to the "preliminary PD", or PsP, scan is observed. Note that any new measurable (>10mm x 10mm) enhancing lesions on the subsequent scan following the "preliminary PD" scan should not be immediately considered "confirmed PD", but instead should be added to the sum of bidimensional products representing the entire enhancing tumor burden.
- 3. Unequivocal and significant worsening neurological examination not attributable to other causes.
- 4. Of note, if there has been a major reduction in steroid dosage in the interval and the patient is felt to be clinically stable or improved, the proper assessment may be "indeterminate" and the therapy could be continued pending the next evaluation.
- 5. Failure to return for evaluation as a result of death or deteriorating condition.

Not Evaluable (NE): Progression has not been documented and one or more sites have not been assessed.

#### 13.8.5 HRQoL

HRQoL will be assessed by the Functional Assessment of Cancer Therapy-Brain (FACT-BR) scale. The FACT-BR (version 4) contains subscales for physical (7-items), functional (7-items), emotional (6-items), and social/family (7-items) well-being. In addition, this instrument contains an 23-item brain cancer subscale (BCS) which assess symptoms commonly reported by brain cancer patients [27]. Cancer-related fatigue will be assessed by the 13-item Fatigue Scale using the Functional Assessment of Cancer Therapy-Fatigue (FACIT-Fatigue) subscale, version 4 [67]. Cognitive problems will be assessed using version 3 of the Functional Assessment of Cancer Therapy-Cognition (FACT-Cog) subscale [68]. This includes subscales for perceived cognitive impairments (20 items), comments from others (4 items), perceived cognitive abilities (9 items), and impact of quality of life (4 items). Beck depression inventory (BDI) will be used to evaluate for underlying depressive symptoms. We will use the revised version (BDI-II) and the scores will range from 0 (no depression) to 63 (severe depression) [69]. The BDI contains 21 questions in regards to mood symptoms and is multiple-choice and self-reported. Exercise behavior will be assessed using the Godin Leisure questionnaire [70]. HRQoL PROs questionnaires will be obtained at screening, after standard RT and TMZ (within 2 to 4 weeks), and approximately every 8 weeks when a subject returns for a Standard of Care visit during adjuvant TMZ.

#### 13.8.6 Cognitive Testing

Cognitive testing will include the performance on the following testing using a computerized battery CNS Vital Signs® [22] (Phase 1) and Brief Assessment of Cognition (BAC) through the NeuroCog app (Phase 2). The CNS Vital Signs® battery consists of seven tests that measure verbal and visual memory, finger tapping, symbol digit coding, the Stroop Test, a test of shifting attention, continuous performance test. Verbal memory test will assess verbal learning, memory for words, immediate recall, and delayed recall. Visual memory tests will assess visual learning, memory for geometric shapes, immediate recall, and delayed recall. Finger tapping test will assess motor speed and fine motor control. Symbol digit coding test will evaluate complex attention, visual-perceptual speed, and information processing speed. Stroop Test will assess executive function, simple and choice reaction time, speed-accuracy trade-off, information processing speed, and inhibition/disinhibition. Shifting attention test will assess executive function, reaction time, and information processing speed. Continuous performance test will assess sustained attention and choice reaction time. Normative data is available for this testing through CNS Vital Signs® and patients' performance will be compared to this normative data. In Phase 2, the BAC battery of tests is implemented through an iPad based app called the BAC App (the vendor that provides this is called VeraSci, previously called NeuroCog) [22]. The table below shows a description of the BAC App Subtests. Examples are included in Appendix E. The verbal responses provided during the tests conducted with the iPad will be audio recorded. These audio recordings will be used by the representatives of the site and sponsor to make sure that your responses are recorded correctly. The audio recordings will be stored and van be viewed later using VeraSci's proprietary portal, which appropriate credentials are needed to access. They will be retained for the period of time specified for all other study data or as required by law. Cognitive testing with the BAC App will be obtained at screening (for the baseline assessment), after standard RT and TMZ (within 2 to 4 weeks), and approximately every 8 weeks when a subject returns for a Standard of Care visit during adjuvant TMZ. If a subject comes off study for disease progression before the approximate 6 and 12 months post completion of treatment timepoint, cognitive testing should still be collected at those timepoints. Additional cognitive testing (HVLT-R, COWA, and TMT) will be performed at these selected times: baseline, standard of care visit before the start of the first cycle of adjuvant temozolomide, and standard of care visits that are 6 and 12 months from the completion of radiotherapy/chemotherapy. These tests will be performed by a trained neuropsychologist or delegate at the clinical center. The tests will include Hopkins Verbal Learning Test-Revised to assess learning, total recall, and memory [71], Trails Making Test Parts A and B to assess attention and executive function [72], and Controlled Oral Word Association Test to assess verbal fluency [73].

Table 5: Description of the BAC App Subtests. Traditional BAC App Battery. List of tests, the domains of cognition they assess, a description of the methodology for assessment and the total time for test administration.

Domain	BAC Subtest	Summary	Duration (mins)
Verbal Memory & Learning	Verbal Memory	Subject is presented with 15 words and asked to recall as many as possible. This procedure is repeated 5 times. Outcome measure : Number of words recalled	7
Working Memory	Digit Sequencing	Subject is presented with auditory clusters of numbers (e.g. 9, 3, 6) of increasing length and asked to tell the rater the numbers in order from lowest to highest. Outcome measure : Number of correct responses	5
Motor Function	Token Motor	Subject is presented with tokens and asked to drag them to a center container as quickly as possible for 60 seconds. Outcome measure : Number of tokens correctly dragged into the container	3
Verbal Fluency	Semantic Fluency	Subject is given 60 seconds to verbally generate as many words as possible in a given category. Outcome measure: Number of words generated	
	Letter Fluency	In two separate trials, subject is given 60 seconds to verbally generate as many words as possible beginning with a given letter of the alphabet. Outcome measure: Number of words generated	5
Speed of Processing	Symbol Coding	Subject is provided a key and asked to fill in the corresponding numbers beneath a series of symbols as quickly as possible within 90 seconds. Outcome measure: Number of correct items	3
Executive Function	Tower of London	Subject is asked to give the minimum number of times the balls in one picture would need to be moved in order to make the arrangement of balls identical to that in the opposing picture. Outcome measure: Number of correct responses	7

#### 13.8.7 Hair Integrity and Hair Loss

Subjective assessments of hair loss will be obtained by the treating provider for subjects at screening (baseline), after standard RT and TMZ finishes (within 2 to 4 weeks), and standard of care (SOC) clinic visit (approximately every 8 weeks) during adjuvant TMZ.

The photographs will be taken of the craniotomy scar (surgical incision site) and can be taken at any angle or background approximately 6-48 inches from the scalp. There will be no identifiers on the photographs. Up to 6 photographs may be taken at any one time point. Photographs will not include the subjects entire face (will not include eyes, nose, mouth). The photographs will be taken by the PI or trained staff and may be uploaded to the electronic medical record, kept in a separate electronic research file or on paper. One photo per timepoint will also be uploaded to the sponsor electronic database. Participation in these pictures is optional for the patient and they can decline the picture taking at any time. Hair loss will be subjectively described and evaluated clinically by the providers treating the patient and later by the sponsor. If the patient is bald, the photos and descriptions may be omitted.

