Secondary	To assess radiographic response in newly diagnosed HGG patients treated with standard RT and TMZ in combination with BMX-001 compared to standard RT and TMZ alone.	Proportion of subjects with complete or partial radiographic response.	See Section 16.5.2
Secondary	To characterize the repeated-dose pharmacokinetic profile of BMX-001 when delivered in combination with RT and TMZ in newly diagnosed HGG patients.	Plasma concentrations and calculated pharmacokinetic parameters (maximum concentration, time to reach maximum concentration, area under the curve, half-life, total body clearance, and volume of distribution) will be determined for BMX-001.	See Section 16.5.2
Exploratory	To describe patient-reported outcomes of HRQoL in newly diagnosed HGG patients treated with standard RT and TMZ in combination with BMX-001 compared to standard RT and TMZ alone.	Mean change from baseline at each follow-up assessment for subscales of the following PROs include Functional Assessment of Cancer Therapy-Brain Cancer (FACT-BR) version 4, Functional Assessment of Cancer Therapy- Fatigue (FACIT-Fatigue) subscale, version 4, Functional Assessment of Cancer Therapy- Cognition (FACT-Cog) subscale, Beck depression inventory (BDI-II), revised version, Godin Leisure questionnaire.	See Section 16.5.3

Exploratory	To describe changes in hair loss in newly diagnosed HGG patients treated with standard RT and TMZ in combination with BMX-001 compared to standard RT and TMZ alone.	Subjective investigator and patient assessment, photographs.	See Section 16.5.3
Exploratory	To describe change in white matter integrity in newly diagnosed HGG patients treated with standard RT and TMZ in combination with BMX- 001 compared to standard RT and TMZ alone.	MRI Brain Diffusion Tensor /Susceptibility Imaging (white matter integrity).	See Section 16.5.3

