#### 16.5.1 **Primary Objective for Phase 2**

The primary goal of this randomized open-label Phase 2 study is to examine the impact of BMX-001 on overall survival, among patients newly diagnosed with HGG who are receiving standard of care (SOC) treatment consisting of daily TMZ and RT.

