4 OVERVIEW OF STUDY DESIGN

The Phase 2 portion of this protocol is a multicenter randomized open-label study comparing the impact of concurrent daily Temozolomide (TMZ) and Radiation Therapy (RT) with BMX-001 (Arm A) versus concurrent daily TMZ and RT alone (Arm B) on survival in patients among patients with newly diagnosed high grade glioma (HGG - WHO grade III and IV). Subjects were randomized with a treatment arm allocation ratio

TREATMENT ARMS

Arm A: Concurrent daily TMZ and RT with BMX-001

Arm B: Concurrent daily TMZ and RT alone

of 1:1, with a goal of enrolling 160 patients in this phase of the study (80 subjects per arm). A permuted block randomization stratified by histologic grade (grade III / IV) and institution will be used to assign patients to treatment with or without BMX-001.

Subjects in Arm A were administered BMX-001 subcutaneously first as a loading dose (28 mg) given 0 to 4 days before the start of chemoradiation and then at subsequent dose (14 mg) twice a week for eight weeks. Subjects in Arm A and Arm B received TMZ dosed at 75 mg/m² orally daily for 42 days and RT delivered in daily fractions of 1.8-2 Gy given 5 days a week for 6 weeks for a total of 59.4-60 Gy.

In all subjects, cognitive performance was measured at the time of enrollment and 2 weeks after the completion of RT, and standard of care (SOC) clinic visits (approximately 8 weeks apart +/- 2 weeks) until death, or patient's choice to discontinue study measures. Cognitive testing was to continue after noted progression until the 12 month follow up timepoint is reached.

In order to characterize the repeated dose pharmacokinetic (PK) profiles of BMX-001 in combination with RT and TMZ in newly diagnosed HGG patients, PK blood samples were drawn on Days 8 and 36 only from the first 6 patients enrolled and assigned to Arm A at a single center (Duke). Measures were obtained at approximately the following times: Pre-

dose, then 0.5 hour, 1 hour, 2 hours, 6 hours and 24 hours post-dose. Samples will be analyzed for BMX-001 using validated analytical methods at the Duke PK lab.

The study's primary phase 2 endpoint is overall survival (OS), defined as the time between randomization and death. A logrank test will be used to compare the survival experience of the two treatment arms. An intent-to-treat philosophy will be used in the analysis of survival by including all patients who are randomized in the analysis. Other analysis sets are defined in this document.

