16 EXPLORATORY OBJECTIVE: HAIR LOSS

The second exploratory objectives is to describe changes in hair loss in newly diagnosed HGG patients treated with standard RT and TMZ in combination with BMX-001 compared to standard RT and TMZ alone.

Subjective assessments of hair loss were obtained by the treating provider for subjects at screening (baseline), after standard RT and TMZ finishes (within 2 to 4 weeks), and standard of care (SOC) clinic visit (approximately every 8 weeks) during adjuvant TMZ.

Qualitative assessments of hair loss depicted in longitudinal subject photographs will be conducted and summarized. Changes observed in Arm A will be compared to those observed in Arm B.

The analyses group for this exploratory objective will include all treated patients who have both assessments of their hair at baseline and at one or more follow-up assessments.

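### The Arm A versus Arm B reading of hair-loss photographs is subjective, the later evaluation falls to the sponsor, and neither document withholds treatment arm from that reader

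*Protocol*

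**What the plan says.** Both documents describe Phase 2 as open-label. Protocol 16.5.1 reads: "The primary goal of this randomized open-label Phase 2 study is to examine the impact of BMX-001 on overall survival". SAP 4 reads: "The Phase 2 portion of this protocol is a multicenter randomized open-label study".

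Hair loss is the second exploratory objective. Protocol Table 2 gives its endpoint as "Subjective investigator and patient assessment, photographs". Protocol 13.8.7 sets out how the data arise:

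- The treating provider makes a subjective assessment at screening, after chemoradiation, and at standard-of-care visits during adjuvant temozolomide.
- Photographs of the craniotomy scar are optional. They may be taken at any angle, from about 6 to 48 inches, and may be omitted if the patient is bald.
- On the images: "There will be no identifiers on the photographs". On their transfer: "One photo per timepoint will also be uploaded to the sponsor electronic database".
- On who judges: "Hair loss will be subjectively described and evaluated clinically by the providers treating the patient and later by the sponsor".

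Protocol 16.5.3.2 and SAP 16 plan a qualitative assessment of the photographs over time. SAP 16 adds: "Changes observed in Arm A will be compared to those observed in Arm B". It restricts the analysis to treated patients with a baseline assessment and at least one follow-up assessment. It does not name the reader, give a scale, or say whether arm is withheld.

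**The concern.** A subjective reading is most vulnerable to expectation when the reader knows, or can find out, which treatment the patient received. Here the trial is open-label, the reading is free-form, and the later evaluation is assigned to the sponsor, which has an interest in the result. If the reader knows the arm, an apparent difference in hair loss could come from the drug or from what the reader expected to see, and the reported summary could not separate the two.

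At stake is whether the exploratory hair-loss comparison can be interpreted. Nothing else in the trial depends on it.

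**Working it through.** No arithmetic applies. The documents attach no test, error rate, effect size or power to hair loss, so there is no figure to reproduce. The check is a comparison of the relevant sections.

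1. **Is a between-arm comparison planned?** Yes, in both Protocol 16.5.3.2 and SAP 16. The objective is worded as descriptive, but the two arms are to be set against each other.

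2. **Is the reading subjective?** Yes. Table 2 and 13.8.7 use that word, and SAP 16 calls the assessment qualitative. No scale is given anywhere.

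3. **Who reads, and can they be masked?** Three sources feed the endpoint.
   - *Treating providers* evaluate hair loss clinically. In an open-label trial with injections in one arm only, they know the arm and cannot be masked.
   - *Patients* also contribute an assessment under Table 2. They know their arm too.
   - *The sponsor* evaluates later. Because photographs are uploaded to its database, this is naturally read as a review of the images. It is the only one of the three that can be masked.

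4. **Is any masking step described for that review?** None appears in Protocol 13.8.7, Protocol 16.5.3.2 or SAP 16. The one blinding procedure in the documents is in Protocol 19.2.1 (Appendix B), where Phase 1 pharmacokinetic samples are labelled with random numbers so that the laboratory does not see patient, timepoint, dose level or cohort. The plan thus masks an instrument assay and leaves a judgement-based reading unaddressed.

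5. **Does the absence of identifiers already mask the reader?** No. That rule sits beside the one against showing the full face and concerns privacy in the image. To be read longitudinally, a photograph in the database has to be linked to a subject and a timepoint, and through the subject it can be linked to an arm.

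6. **Would masking to arm work?** It should. The photographs show the scalp at the incision, whereas Protocol 9.1.2 places the injections on the torso, upper leg or upper arm. Injection-site discoloration, listed among the common effects in Protocol 5.6.2, should be outside the frame.

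7. **Can it still be done?** SAP 16 puts the provider assessments in the past tense and the photograph review in the future tense. On that wording, the method of review can still be specified.

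**The case against.** The strongest objection is that little turns on this. The objective is exploratory and descriptive. The reasoning on whether to develop the drug further (Protocol 16.5.5.1, SAP 8.4.1) names relative toxicity and ease of administration alongside the survival test, and does not mention hair loss. The list of outputs in SAP 19 contains no hair-loss table. All of this stands, and it limits the importance of the point. It does not remove it, because the comparison is still planned and, where a masked reading is cheap, an unmasked one is the weaker choice.

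It can also be said that the DSMB-Plus reviews the study for bias in endpoint assessment and for financially linked bias (Protocol 15.1.1). That is a partial safeguard, but it is oversight of conduct and reporting and does not keep arm from the reader.

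Four stronger readings are tempting and are not supported:

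- *The sponsor's reader is unmasked.* The documents do not say so. They are silent, and SAP 16 does not say who reads. What can be said is that masking is not specified.
- *Treating providers rate the photographs unmasked.* Protocol 13.8.7 has them evaluate clinically. Their knowledge of arm follows from the open-label design and is not something the SAP can repair.
- *The whole between-arm signal passes through a photograph reader.* Table 2 also counts patient and investigator assessment.
- *The photographs are effectively masked already, so no new step is needed.* As shown above, an image without identifiers is still linked to a subject record.

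Masking the reader to visit order, or imposing a particular rating scale, would go further than the concern requires. The plan is to read change within a patient, so each patient's photographs belong together, and scar healing may reveal the order anyway. A photograph of the incision site may not show enough scalp to support a grade such as complete loss.

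**Conclusion.** The concern holds in a limited form. In an open-label trial, the planned comparison of hair-loss photographs rests on a subjective reading, the later evaluation is given to the sponsor, and neither document withholds treatment arm from that reader. The comparison is therefore open to expectation bias.

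The direction and size of any bias cannot be estimated from the documents. The effect is limited to one exploratory endpoint with no test, success rule or listed table. Overall survival, the secondary endpoints and all stated power calculations are unaffected. This is an inexpensive improvement, not a flaw in the trial's main conclusions.

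The conclusion assumes that the sponsor's later evaluation is the photograph review planned in SAP 16, and that no masking procedure for it exists in a document outside the protocol and SAP.

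**What to change.** Add to SAP 16:

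- The sponsor's existing photograph review is done on coded image sets. Each patient's photographs stay together, so that change can be read, and patients are presented in random order.
- Treatment arm is withheld from the reader until the ratings are locked.
- This masked reading is used for the Arm A versus Arm B comparison. The unmasked provider and patient assessments are reported as supportive.

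The cost is a few sentences in the SAP and a small step to export, unlink and code the database images. No reader, visit or data collection is added. The change does not address the optional nature of the photographs, their unstandardised angle and distance, or their omission for bald patients; those limits should be stated when the result is reported.
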